4 STUDY DESIGN

This is a multi-center, randomized, double-blind, placebo-controlled, superiority clinical trial evaluating short course (5 day) vs. standard course (10 day) of oral beta-lactam antibiotic therapy (amoxicillin, amoxicillin-clavulanate, cefdinir) for treatment of CAP in children 6-71 months of age who have clinically improved prior to enrollment. The study will randomize approximately 400 enrolled subjects to one of the two study arms (approximately 200 children in each arm) in order to reach 360 subjects completing Outcome Assessment Visit 1. Subjects will be randomized (1:1) to receive either a standard course of the initially prescribed antibiotic (10 days) or a short course of the initially prescribed antibiotic (5 days) plus 5 days of matching placebo.

The study will recruit potential subjects from children who are diagnosed with CAP and who are initiated on oral beta-lactam therapy (amoxicillin, amoxicillin-clavulanate, cefdinir) by healthcare providers in EDs, outpatient clinics, and urgent care centers at the study sites. Day -5 is defined as the date on which oral beta-lactam therapy is initiated for a diagnosis of CAP. Potential subjects will be identified at any time following clinical diagnosis of pneumonia. These subjects will be assessed for eligibility and enrolled on Day -3 to -1 of their initially prescribed oral beta-lactam therapy. Subjects may also be enrolled on Day 1 (the first day of receipt of study agent) provided they have not yet received any doses of the healthcare provider-prescribed antibiotic therapy for that day.

A Schedule of Events is provided in Appendix A.

Visit 1: Enrollment Visit. Subjects who meet the eligibility criteria, and whose parent/guardian consents for participation in the study, will complete an Enrollment Visit on Day -3 to -1. Subjects satisfying the inclusion criteria with no exclusion criteria will be enrolled and randomized. Enrolled subjects will continue to receive the initially prescribed antibiotic through Day -1. The subjects' parents/guardians will be instructed to contact study personnel if their child develops fever or worsening respiratory symptoms (worsening cough, increased work of breathing, any other concerning symptoms in the parents' estimation) following enrollment.

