4. INVESTIGATIONAL PLAN

4.1. Overall Study Design and Plan

This is a multi-center, randomized, double-blind, placebo-controlled, superiority clinical trial evaluating short course (5 day) vs. standard course (10 day) of oral beta-lactam antibiotic therapy (amoxicillin, amoxicillin-clavulanate, cefdinir) for treatment of CAP in children 6-71 months of age who have clinically improved prior to enrollment. The study will randomize approximately 400 enrolled subjects to one of the two study arms (approximately 200 children in each arm) in order to reach 360 evaluable subjects. Subjects will be randomized (1:1) to receive either a standard course of the initially prescribed antibiotic (10 days) or a short course of the initially prescribed antibiotic (5 days) plus 5 days of matching placebo.

The study will recruit potential subjects from children who are diagnosed with CAP and who are initiated on oral beta-lactam therapy (amoxicillin, amoxicillin-clavulanate, cefdinir) by healthcare providers in EDs, outpatient clinics, and urgent care centers at the study sites. Day -5 is defined as the date on which oral beta-lactam therapy is initiated for a diagnosis of CAP. Potential subjects will be identified at any time following clinical diagnosis of pneumonia. These subjects will be assessed for eligibility and enrolled on Day -3 to -1 of their initially prescribed oral beta-lactam therapy. Subjects may also be enrolled on Day 1 (the first day of receipt of study agent) provided they have not yet received any doses of the healthcare provider-prescribed antibiotic therapy for that day.

Visit 1: Enrollment Visit. Subjects who meet the eligibility criteria, and whose parent/guardian consents for participation in the study, will complete an Enrollment Visit on Day -3 to -1. Subjects satisfying the inclusion criteria with no exclusion criteria will be enrolled and randomized. Enrolled subjects will continue to receive the initially prescribed antibiotic through Day -1. The subjects' parents/guardians will be instructed to contact study personnel if their child develops fever or worsening respiratory symptoms (worsening cough, increased work of breathing, any other concerning symptoms in the parents' estimation) following enrollment.

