5. SAMPLE SIZE CONSIDERATIONS

The null hypothesis corresponding to the primary analysis of this study is:

H0: The sum of the probability that a subject assigned to the 5-day arm will have a higher DOOR than if assigned to the 10-day arm plus one-half the probability of equal DOORs is 50% (i.e., no difference in DOOR).

The primary study sample size is based on a superiority test of the null hypothesis above, under an assumed alternative hypothesis that the sum of the probability that a subject assigned to the 5-day arm will have a higher DOOR than if assigned to the 10-day arm plus one-half the probability of equal DOORs is 60% (p=60%).

A sample size of 360 (180 per arm) provides 90% power using a 2-sided alpha=0.05 with a Wilcoxon Mann-Whitney U test (see calculation below). If p=65% or 70%, then a total sample size of 160 (80 per arm) or 90 (45 per arm), respectively, would be required. The sample size is inflated by ~10% based on an estimate from a similar study, in order to account for loss to follow-up resulting in a total sample size of 400 (200/arm).

Sample size calculations were based on the formula below (Noether 1987):

$$N = \frac{(z_{\alpha} + z_{\beta})^2}{12c(1-c)\left(p'' - \frac{1}{2}\right)^2}$$

$$z_{\alpha} = \Phi^{-1}(0.975); z_{\beta} = \Phi^{-1}(0.90); (90\% \text{ power for two-sided test with } 5\% \text{ Type I error})$$

$$c = 0.5 \text{ (equal allocation to treatment arms)}$$

$$p'' = 0.6 \text{ (Pr(Higher DOOR) under alternative hypothesis)}$$

Note that the primary analysis statistical methods use the ITT analysis population and will account for missing data with multiple imputation. The exact analysis method was not used for the power calculation because it would require an excessive amount of assumptions about the nature and patterns of missing data in the final dataset and relationships of components of the imputation model to the primary outcome. Instead, a complete case analysis assuming 90% evaluable for analysis was used to obtain approximately 90% power in the actual analysis.

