6.6.1. Predicted Interval Plots (PIPs)

PIPs provide insight into the range of possible outcomes that can be expected for the final primary analysis under various assumptions (such as that the current observed treatment effect represents the true effect or that the null hypothesis represents the true effect). Using various assumptions, data is simulated from theoretical distributions to create multiple complete datasets representing complete datasets for the final analysis under the assumed reality. Details of PIPs and their interpretations can be found in the literature (Evans 2007, Li 2009).

For each assumption, one-hundred (100) 95% predicted intervals of the probability of higher DOOR in the 5-day treatment course at Outcome Assessment Visit #1 will be generated from 100 complete datasets. Each dataset will include the ITT analysis population for the interim analysis, plus additional simulated subjects to a total of 400 subjects in the dataset. Predicted intervals will be computed by inverting the Mann-Whitney U test (Section 8.2.2). The predicted intervals will be ordered by their corresponding point estimate of the probability of higher DOOR in the 5-day treatment course and shown graphically as forest plots. The 95% confidence interval generated in the ITT interim analysis of the probability of higher DOOR at Outcome Assessment Visit #1 will be overlaid on the forest plot. Comparisons of the predicted intervals to

the confidence interval show changes in precision of estimated probability (tightness of predicted intervals versus the confidence interval) as well as the expected distribution of location shifts of the estimated probability in the final analysis relative to the interim analysis, dependent on the assumptions used. Conditional power will be estimated as the percentage of predicted intervals with a lower bound that is greater than 0.5.

Three assumptions will be included in the PIPs: 1) current trend, 2) null hypothesis, and 3) alternative hypothesis. Further assumptions may be explored depending on results of the ITT analysis of the primary endpoint but will not be pre-specified.

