Under the current trend assumption, each complete dataset is simulated in the following way. Multiple imputation will be used (Section 8.4.1) to create 100 datasets with complete data for DOOR at Outcome Assessment Visit #1 for enrolled subjects. For each of these 100 datasets, future subjects will be added to the analysis dataset. The number of future subjects added will be chosen to bring the total number of subjects (real and simulated combined) to 400 in the analysis dataset. The treatment ratio in the simulated subjects will be 1:1. The DOOR values for the future subjects in each dataset will be simulated by sampling with replacement from the empirical distribution of DOOR values by treatment from the same dataset.

Under the null hypothesis assumption, each complete dataset is simulated in the following way. Multiple imputation will be used (Section 8.4.1) to create 100 datasets with complete data for DOOR at Outcome Assessment Visit #1 for enrolled subjects. For each of these 100 datasets, future subjects will be added to the analysis dataset. The number of future subjects added will be chosen to bring the total number of subjects (real and simulated combined) to 400 in the analysis dataset. The treatment ratio in the simulated subjects will be 1:1. The DOOR values for the future subjects in each dataset will be simulated by sampling with replacement from the overall (not by treatment) empirical distribution of DOOR values from the same dataset.

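### The predicted interval plots treat all 400 children as fully observed, so the conditional power shown to the DSMB runs high, by about 5 points at worst

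*SAP*

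**What the plan says.** SAP 6.6.1 generates 100 datasets under each of three assumptions (current trend, null, alternative). Each holds the interim ITT children "plus additional simulated subjects to a total of 400 subjects in the dataset". The instruction is repeated for every assumption: "The number of future subjects added will be chosen to bring the total number of subjects (real and simulated combined) to 400". Future children receive a DOOR by resampling, and nothing in the section makes any of them missing. Interim children with missing DOOR enter each dataset with one imputed value. The predicted interval comes from inverting the ordinary Mann-Whitney test (SAP 8.2.2), and conditional power is the share of intervals lying wholly above 0.5.

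Elsewhere the plan expects losses. Protocol section 4 randomizes about 400 "in order to reach 360 subjects completing Outcome Assessment Visit 1", and SAP 4.1 does so "in order to reach 360 evaluable subjects". In SAP 5, "A sample size of 360 (180 per arm) provides 90% power using a 2-sided alpha=0.05 with a Wilcoxon Mann-Whitney U test", and "The sample size is inflated by ~10% based on an estimate from a similar study". SAP 5 also explains how planned power relates to the ITT analysis with imputation: "a complete case analysis assuming 90% evaluable for analysis was used to obtain approximately 90% power in the actual analysis". That primary analysis (SAP 8.1.1) uses 20 imputations and adds a between-imputation term to the variance.

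**The concern.** The plots are meant to show the DSMB what the final primary analysis is likely to give. That analysis will have about 400 children in the ITT cohort but a real DOOR for only about 360 of them, and Rubin's rules will widen its interval accordingly. The predicted intervals carry no such penalty.

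The omission works in two places. The predicted intervals are too narrow, and the simulated future estimates vary too little. SAP 6.6.1 also overlays the interim ITT interval and invites a comparison of precision. Part of the apparent tightening comes from dropping the imputation variance and not from added children.

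At stake is the conditional power that the DSMB will read when it considers futility.

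**Working it through.** **Inputs.** Two-sided alpha 0.05, power 90%, alternative 0.60 against 0.50, 360 evaluable, about 10% loss (SAP 5); fill to 400 (SAP 6.6.1); interim at about 30% (SAP 6.6). Ties are ignored, as in the SAP's sample size formula.

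**Reproducing the plan.** The SAP 5 formula gives N = (1.960 + 1.282)² / (12 × 0.25 × 0.10²) = 350.2. For 0.65 and 0.70 it gives 155.7 and 87.6. The stated 360, 160 and 90 are these figures rounded up, all within 3%. Power at 360 is 90.8%, and 360/0.9 = 400. With 400 fully observed, power would be 93.4%.

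**Interval width.** √(400/360) = 1.054. The half-width is 1.96/√(3 × 400) = 0.0566 as written and 1.96/√(3 × 360) = 0.0596 for 360, so the interval is about 5% too narrow.

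**Conditional power.** Take the variance of the estimate as 1/(3N), n interim children, f = n/N, interim estimate a and future value b:

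CP = Φ{ [f·a + (1−f)·b − 0.5 − 1.96/√(3N)] / [(1−f)/√(3(N−n))] }

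As written, n = 120 and N = 400. With 10% missing throughout and nothing recovered by imputation, n = 108 and N = 360. Example with a = 0.50 and b = 0.60:
- 400: (0.0700 − 0.0566)/0.0242 = 0.556, so CP = 71.1%
- 360: (0.0700 − 0.0596)/0.0255 = 0.407, so CP = 65.8%

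| Assumption | Interim estimate | As written (400) | 360 | Excess, points |
|---|---|---|---|---|
| Current trend | 0.56 | 55.6% | 50.6% | 5.1 |
| Current trend | 0.57 | 71.1% | 65.8% | 5.3 |
| Current trend | 0.60 | 96.4% | 94.4% | 2.0 |
| Alternative | 0.50 | 71.1% | 65.8% | 5.3 |
| Alternative | 0.55 | 88.0% | 84.0% | 4.0 |
| Null | 0.50 | 1.0% | 1.0% | 0.0 |
| Null | 0.60 | 13.6% | 12.2% | 1.3 |

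(Excess is taken from unrounded values.) The current-trend maximum is 5.3 points, at an interim estimate of about 0.567 (66.7% against 61.4%).

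**What the imputed analysis is worth.** A simulation used 1,500 trials of 400 children with 10% missing completely at random, 20 linear-regression imputations and the SAP 8.1.1 combination. It gave an effective N of about 364 with no useful auxiliary data, about 372 with an auxiliary correlation of 0.5, and about 385 with 0.8. The correlations are assumptions. At a true value of 0.565, power was 60.6% fully observed, 55.5% complete case and 55.9% imputed without auxiliary data. Putting N = 364, 372 and 385 into the formula for the worked example gives 66.4%, 67.4% and 69.2%, an excess of about 4.7, 3.6 and 1.9 points.

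**Sensitivity of the ceiling.** If all 120 interim children were observed and only the 280 simulated ones lost 10% (120 + 252 = 372), the worked example becomes 64.4%, an excess of 6.7 points, because the future data then carry less weight; the current-trend maximum falls to 3.5. With the look at half the trial (200 of 400 against 180 of 360) the maximum is 6.2.

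**The case against.** Filling to 400 is not an inconsistency. The primary analysis is ITT: SAP 6.3.1 keeps randomized children who were still eligible on Day 1 and imputes what is missing, and the note to SAP Figure 2 treats all enrolled children as evaluable for it. A reader might infer that the plots should stop at 360. The documents do not support that, since 360 is the expected number with an observed outcome and not the size of the ITT cohort. SAP 6.6.1 also says openly that its simulated datasets are complete.

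Nor is 360 established as the information in the final analysis. SAP 5 uses the complete-case figure as a stand-in because the exact calculation would need too many assumptions. The imputation model in SAP 8.4.1 can draw on the Visit #2 ordinal response and daily severity scores, and SAP 6.5 allows DOOR to be defined when some components are missing. Each of the 100 datasets also carries a different imputation, so interim imputation uncertainty does enter the spread of predicted estimates; it is absent only from the interval width.

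Finally, with 100 datasets the Monte Carlo standard error is √(0.5 × 0.5/100) = 5.0 points at 50% and 4.6 points at 70%, about as large as the bias.

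All of this stands, and it limits the size of the point. It does not remove it. Monte Carlo error is random and shrinks with more datasets. The omitted missingness pushes the positive scenarios in one direction and stays however many datasets are run.

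**Conclusion.** The point holds as a minor one. The headcount is right; treating all 400 as observed, with an interval that omits imputation variance, is not. Predicted intervals are up to about 5% too narrow. Conditional power is too high by at most about 5 points when it lies near 50-70% and imputation recovers nothing, and by about 2-4 points there if effective N is 372-385. The excess is about 2 points at a current trend of 0.60, and 0-1.3 points under the null assumption for interim estimates of 0.50 to 0.60.

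These sizes assume 10% missing in both interim and future children, a look at about 30%, and no ties. The sensitivity figures show that the ceiling moves somewhat if those assumptions change.

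A reader might infer that a stopping decision or the error rate is compromised. The documents do not support that. Neither gives a conditional-power threshold for futility, and stopping for efficacy depends only on p < 0.001 in the interim ITT test. What is affected is a figure that the DSMB reads alongside the plots and component summaries.

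**What to change.** Under all three assumptions in SAP 6.6.1, keep the total at 400 and set DOOR to missing in the simulated future children. Use the planning rate of 10%, or the rate among interim children whose Visit #1 window has closed. The raw interim missing fraction should not be used: the snapshot includes all enrolled children (SAP 6.6), so those whose visit is still pending would count as missing. Then impute and compute each predicted interval by SAP 8.1.1 with Rubin's rules. Basing the interval on observed children alone would predict a complete-case analysis, which is not the primary one.

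A simpler approximation keeps 400 and scales the interval to about 360 effective children, multiplying its width by 1.054. The DSMB should be told that this is meant as a conservative bound. If neither is done, the DSMB report should at least say that the plots assume no missing DOOR.

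The cost is a sentence or two in the SAP, a few lines of simulation code, somewhat more computation (20 imputations within each of 100 datasets per assumption), and slightly less favourable conditional power.

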6.6. Interim Analyses and Data Monitoring

One interim analysis, described below, will be performed by the SDCC statistician responsible for this protocol and reported to the DSMB after approximately 30% of the targeted subjects have completed the study. The interim analysis will inform DSMB decisions regarding stopping early for efficacy, futility, or safety. Only the SDCC statistician and the DSMB will see the interim analysis report.

For the interim analysis, a snapshot of the study database will be unblinded and used to conduct analyses as follows. An ITT analysis including all enrolled subjects in the snapshot of the study database will be performed, testing the null hypothesis (H_0 : Probability of higher DOOR in short course + $\frac{1}{2}$ probability of equal DOOR = 0.5) using the methods described in Section 8.1.1, with the modification that the Haybittle-Peto boundary ($p < 0.001$) will be used when concluding statistical significance. The study may be stopped early for efficacy only if statistical significance is detected in that test. In the event of statistical significance, sensitivity analyses using complete case and according-to-protocol cohorts (CC-V1 and ATP-V1, as described below) as well as worst case analyses will be included in the DSMB report to further guide decisions for stopping for efficacy.

A 95% confidence interval for the probability that a randomly selected subject will have a better DOOR if assigned to the 5-day strategy (vs. the standard strategy) will be estimated but not used to inform DSMB decisions about stopping early for efficacy. Predicted interval plots (PIPS, Section 6.6.1) will be constructed to provide the DSMB with a prediction of the trial results were the trial to continue as planned under varying assumptions regarding future data (e.g., current trend continues, null hypothesis is true, alternative hypothesis is true). In order to assess whether the 5-day strategy is differentially effective in subgroups of subjects, 95% confidence intervals for the probability of higher DOOR (as well as p-values for the test of a probability of higher DOOR of 0.5) when assigned to the short course of antibiotics will be shown as forest plots comparing each stratification variable (age < 2 years, age ≥ 2 years, ED as the initial treatment site, out-patient or urgent care as the initial treatment site, amoxicillin as the initial antibiotic, amoxicillin-clavulanate as initial antibiotic, and cefdinir as initial antibiotic).

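### Conditional power at the interim is a percentage of only 100 simulated intervals per assumption, so it carries an avoidable simulation error of about 6 to 10 points over most of its range

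*SAP*

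**What the plan says.** SAP section 6.6 plans one interim analysis, "reported to the DSMB after approximately 30% of the targeted subjects have completed the study". On its purpose it states: "The interim analysis will inform DSMB decisions regarding stopping early for efficacy, futility, or safety".

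Section 6.6.1 describes the predicted interval plots. The count is fixed there: "For each assumption, one-hundred (100) 95% predicted intervals of the probability of higher DOOR in the 5-day treatment course". The assumptions are also fixed: "Three assumptions will be included in the PIPs: 1) current trend, 2) null hypothesis, and 3) alternative hypothesis". For each assumption the enrolled subjects are first completed by imputation: "Multiple imputation will be used (Section 8.4.1) to create 100 datasets with complete data for DOOR at Outcome Assessment Visit #1 for enrolled subjects". Each imputed data set then receives one set of simulated future subjects, which brings it to 400. Conditional power is read off the same simulations: "Conditional power will be estimated as the percentage of predicted intervals with a lower bound that is greater than 0.5".

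The Protocol's section on the interim analysis of efficacy, futility and safety mentions the plots but not conditional power. Neither document gives a simulation error, a separate count for conditional power, or a seed for drawing future subjects. Neither gives a conditional-power value below which the trial would be judged futile.

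**The concern.** A hundred intervals are enough for a plot, where the eye takes in location and spread. A probability estimated from the same hundred is coarser. It moves in whole percentage points and depends noticeably on the random numbers drawn. Two runs of the same program on the same interim data could give the DSMB different figures.

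The efficacy decision has a defined rule (p<0.001 on the ITT test). Futility is left to the board's judgement, and conditional power is the one number in the report that states a chance of eventual success. Simulation noise in it can be removed, whereas the sampling uncertainty of an interim at about 30% cannot.

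The SAP is more careful elsewhere. Section 8.2.2 uses 10,000 resamples for bootstrap intervals of the same Mann-Whitney statistic, and section 8.4.1 fixes seeds and ordering so that imputations can be replicated.

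**Working it through.** **Inputs.** R = 100 simulated data sets per assumption, each giving a yes or no (lower bound above 0.5), from SAP 6.6.1. The plan states no simulation error, so there is no figure of its own to reproduce on this point.

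**Formula.** Given the interim data, each replicate uses its own imputed data set and its own future subjects, so the replicates can be treated as independent. With true conditional power c, SE = √(c(1−c)/R), and the 95% half-width is 1.96 × SE.

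**R = 100.**

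| True c | SE (points) | 95% half-width (points) |
|---|---|---|
| 5% or 95% | 2.2 | 4.3 |
| 10% or 90% | 3.0 | 5.9 |
| 20% or 80% | 4.0 | 7.8 |
| 30% | 4.6 | 9.0 |
| 50% | 5.0 | 9.8 |

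Exact binomial limits agree: 10/100 gives 4.9–17.6%, 20/100 gives 12.7–29.2%, and 50/100 gives 39.8–60.2%. A result of 0/100 has an upper limit of 3.6%.

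**Two runs on the same data.** The SE of their difference is √2 × SE. At 20% this is 1.414 × 4.0 = 5.7 points (95% of differences within 1.96 × 5.7 ≈ 11). At 50% it is 1.414 × 5.0 = 7.1 points (within about 14).

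**Check by simulation.** The current-trend procedure was repeated 200 times on fixed interim data, assuming 60 per arm at the interim, 140 per arm resampled, and no missing data. At a true 18% the 100-interval estimate had SD 3.8 points and a 95% range of 12–26%. At a true 62% it had SD 4.9 points and a range of 54–72%. Both match the formula.

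**More replicates, worst case c = 50%.** The half-width is 3.1 points at R = 1,000, 2.0 at 2,500 and 1.0 at 10,000. Solving 0.25 × (1.96/h)² gives R = 2,401 for h = 2 points and 9,604 for h = 1 point.

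**Reusing the 100 imputed data sets.** If K sets of future subjects are drawn per imputed data set, the variance is s²/100 + (c(1−c) − s²)/(100K), where s is the SD of conditional power between imputed data sets. The documents do not give s, so a range is assumed, with c = 50%:

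| s | K = 25: half-width | K = 100: half-width |
|---|---|---|
| 0 | 2.0 points | 1.0 point |
| 5 points | 1.96 × √(0.000025 + 0.000099) = 2.2 points | 1.96 × √(0.000025 + 0.000025) = 1.4 points |
| 10 points | 1.96 × √(0.000100 + 0.000096) = 2.7 points | 1.96 × √(0.000100 + 0.000024) = 2.2 points |

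All are well below 9.8 points.

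**The case against.** The strongest reply is that this number decides nothing by rule. Efficacy stopping rests only on p<0.001, which does not use these simulations. With no futility cut-off, an error of a few points cannot reverse a prespecified action. The DSMB charter is not among the documents, so how the board would use the figure is unknown. All of this stands, and it is why the point is minor.

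A reader might infer that conditional power is the board's only quantitative evidence on futility. The documents do not support that. SAP 6.6 and 6.6.1 also give the board the ITT estimate and p-value, a 95% CI (barred only from efficacy decisions), subgroup intervals, component risk differences, and the predicted intervals with the interim CI overlaid.

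A second reply is that interim sampling error is much larger. With 60 per arm, no ties and no missing data, the SE of the interim probability is √(121/(12 × 60 × 60)) = 0.053. In a simulation of the current-trend procedure, conditional power was about 1% for an interim estimate of 0.50, 39% for 0.55 and 96% for 0.60. This is right about scale and limits how much is gained. It does not justify adding noise that can be removed cheaply.

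A third reply is that the error is smaller where futility would be clear: 4.3 points at a true 5%, and 0/100 still rules out values above 3.6%. That also stands. A plainly futile trial would be recognised with 100 intervals, and the loss of precision matters for intermediate values.

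**Conclusion.** The point holds as a minor matter of precision. With 100 intervals, conditional power has a 95% simulation error of about 6 to 8 points at a true 10–20% and at most about 10 points, reached near 50%. The 10–20% range is an assumption about where futility might be debated, since the plan names no threshold. The calculation treats the 100 replicates as independent given the interim data. Under the alternative assumption the shift is tuned on those same data sets, so the error there may differ slightly.

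It would be tempting to conclude that the DSMB could be led to a wrong stop. The documents do not show that: no stopping rule depends on this figure, and the board has other evidence. Type I error and the primary analysis are untouched.

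**What to change.** In SAP 6.6.1, separate the plot from the probability. Keep 100 intervals per assumption for the plot. Compute conditional power under each assumption from several thousand simulated data sets: about 2,400 gives ±2 points at worst, and about 10,000 gives ±1 point. State the count, the simulation error and a seed.

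One practical route keeps the 100 imputed data sets and draws many sets of future subjects for each, for example 25 (2,500 in all) or 100 (10,000 in all), using the first draw from each for the plot. If conditional power varies much between imputed data sets, increase the number of imputations too. For the alternative, tune the shift once and then hold it fixed for all draws.

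The cost is computing time plus a small edit, because the section now ties each replicate to its own imputed data set and tunes the shift across the 100. No endpoint, alpha, sample size or trial conduct changes. If the interim has already been held, report the simulation error beside the figure or rerun it with more draws.
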